1.2 DRUG PROFILE

1.2.1 BI 1358894

For a detailed description of the BI 1358894 profile, please refer to the current Investigator's Brochure (IB) [[c10354149](#)].

Pharmacokinetics in Humans

Human PK data are currently available from the FIM study 1402-0001, which consisted of an SRD part (tested doses: 3 mg – 200 mg BI 1358894) and of a food effect part (tested doses: 50 mg and 100 mg BI 1358894 under fasted and fed conditions) [[c24903142](#)].

Following oral administration of film-coated tablets in fasted state BI 1358894 reached maximum plasma concentrations after 1 to 5 hours. Thereafter BI 1358894 plasma concentrations declined in a multiphasic fashion implying multi-compartmental distribution and exhibited a long terminal phase, which seems to be dose-independent.

C_{max} , AUC_{0-72} and $AUC_{0-\infty}$ of BI 1358894 increased in a dose dependent way. Preliminary statistical evaluation showed that the increase in C_{max} and AUC_{0-72} was less than dose proportional. $AUC_{0-\infty}$ increased slightly less than dose proportional when given without food.

Also the food effect was dependent on the administered dose. While the exposure of BI 1358894 increased by factor 1.6 for the 50 mg dose, a food effect of factor 2.5 was observed for the 100 mg dose.

After completion of the food effect assessment, a dose of 200 mg BI 1358894 has been given after a high-calorie, high-fat meal in the SRD part of 1402-0001 [[c24903142](#)]. Compared to the cohort receiving 200 mg under fasted conditions, food increased exposure by about 2.4-fold (exposure of 200 mg BI 1358894, fed conditions: $C_{max} = 857 \text{ nM}$, $AUC_{0-24} = 11640 \text{ nM} \cdot \text{h}$).

Based on PK data of previous dose groups (DGs) in the 200 mg fed DG PK blood sampling was extended to 672 h. Sampling from 240 h to 672 h revealed another phase with low plasma concentrations and long terminal half-life of about 200 h. The proportion of AUC beyond 192 h is less than 20% of total AUC. Hence, it is not expected that this phase markedly contributes to accumulation or steady state attainment.

Preliminary PK data from the MRD study 1402-0002 [[c28667517](#)] support this observation. In the first dose groups (10 mg and 25 mg), an accumulation ratio (based on AUC_{0-24}) of 2.5 was observed. Steady state seems to be achieved after about 2 weeks. Both accumulation ratio and approximation of steady state attainment are in line with an effective half-life of ~50 to 70 h.

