1.2.2 Residual Effect Period

Based on an effective half-life of 50 to 70 h the Residual Effect Period (REP) of BI 1358894 has been determined to be 14 days. This is the period after the last dose with measurable drug levels and/or pharmacodynamic effects is still likely to be present.

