7.3.4 Safety analyses

Safety will be analysed based on the assessments described in Section [2.2.2.2](#). All treated subjects (TS, refer to Section [7.2](#)) will be included in the safety analysis. Safety analyses will be descriptive in nature and based on BI standards. No hypothesis testing is planned.

For all analyses, the treatment actually administered (= treatment at onset) to the subject will be used (any deviations from the randomised treatment will be discussed in the minutes of the Report Planning Meeting).

Proprietary confidential information © 2020 Boehringer Ingelheim International GmbH or one or more of its affiliated companies

Treatments will be compared in a descriptive way. Tabulations of frequencies/proportions will be used to evaluate categorical (qualitative) data, and tabulations of descriptive statistics will be used to analyse continuous (quantitative) data.

Measurements (such as ECG, vital signs, or laboratory parameters) or AEs will be assigned to treatments (see Section [4.1](#)) based on the actual treatment at the planned time of the measurement or on the recorded time of AE onset (concept of treatment emergent AEs). Therefore, measurements planned or AEs recorded prior to first intake of trial medication will be assigned to the screening period, those between first trial medication intake and end of REP (see Section [1.2.2](#)) will be assigned to the treatment period. Events occurring after the REP but prior to next intake or end of trial termination date will be assigned to 'follow-up'. In case of two or more treatments, the follow-up will be summarized according to the previous treatment. These assignments including the corresponding time intervals will be defined in detail in the TSAP. Note that AEs occurring after the last per protocol contact but entered before final database lock will be reported to Pharmacovigilance only and will not be captured in the trial database.

Additionally, further treatment intervals (analysing treatments) may be defined in the TSAP in order to provide summary statistics for time intervals, such as combined treatments, on-treatment totals, or periods without treatment effects (such as screening and follow-up intervals).

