6. GENERAL ANALYSIS DEFINITIONS

6.1 TREATMENTS

For basic study information on treatments to be administered, assignment of treatment groups, and selection of doses, cf. Section 4 of the CTP.

The trial consists of Part 1 and Part 2 and the two parts will be analysed separately.

In Part 1, subjects are planned to be treated with a single dose of BI 1358894 mixed with [14C] BI 1358894.

For statistical analyses of AEs, safety laboratory data, and vital signs the following separate analysis phases will be defined for each subject:

Table 6.1: 1 Part 1 - Analysis phases for statistical analysis of AEs, safety laboratory data and vital signs

Study analysis phase	Label	Start (inclusive)	End (exclusive)
Screening	Screening	Date of informed consent	Date/time of administration of study drug
On-treatment	BI 1358894 SD	Date/time of administration of study drug	Date/time of administration of study drug + REP (14 days * 24 h)
Follow-up	F/U BI 1358894 SD	Date/time of administration of study drug + REP (14 days * 24 h)	12:00 a.m. on day after trial completion date

SD = Single Dose

In Part 2, subjects are planned to be treated with multiple dose of 100 mg BI 1358894 as 2 film-coated tablets once daily (2 tablets x 50 mg, q.d.) from Day 1 to Day 21.

Table 6.1: 2 Part 2 - Analysis phases for statistical analysis of AEs, safety laboratory data and vital signs

Study analysis phase	Label	Start (inclusive)	End (exclusive)
Screening	Screening	Date of informed consent	Date/time of first administration of study drug
On-treatment	BI 1358894 MD	Date/time of first administration of study drug	Date/time of last administration of study drug + REP (14 days * 24 h)
Follow-up	F/U BI 1358894 MD	Date/time of last administration of study drug + REP (14 days * 24 h)	12:00 a.m. on day after trial completion date

MD = Multiple Doses

AE displays in CTR Section 15.3, Appendix 16.1.13.1.8.2 and Appendix 16.1.13.1.8.3 will present results for the on-treatment phase only.

More details on the technical implementation of these analyses are provided in the ADS Plan of this TSAP.

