For disclosure of AE data in the EudraCT register, the frequency of AEs, the frequency of non-serious AEs with an incidence of greater than 5 % (in preferred terms) and the frequency of SAEs will be summarised.

For support of lay summaries, the frequency of subjects with drug-related SAEs will be summarized by treatment, primary SOC and preferred term.

If the subject reports headaches during the treatment period further information about the duration of headache, location, characteristics, and signs and symptoms were recorded. These data will be summarized with descriptive statistics. Headache episodes with onset during screening and Follow-up phase will be listed only.

7.8.2 **Laboratory data**

The analyses of laboratory data will be descriptive in nature and will be based on BI standards "Display and Analysis of Laboratory Data" (9).

Analyses will be based on normalised values, which means transforming to a standard unit and a standard reference range. The original values will be analysed if the transformation into standard unit is not possible for a parameter.

Descriptive statistics of laboratory values over time and for the difference from baseline (see [Section 6.7](#)) will be provided for the on-treatment phase. Frequency tables of changes between baseline and last value on treatment with respect to the reference range will be presented. Qualitative urinalysis results will be listed only.

CTP Section 7.3.4: *Values outside the reference range as well as values defined as possibly clinically significant will be highlighted in the listings.*

Unscheduled measurements of laboratory data will be assumed to be repeat measurements of the most recent scheduled measurement (e.g. for follow-up or confirmation of a particular value). Therefore, unscheduled measurements will be assigned to the planned time point of the previous scheduled measurement. Descriptive statistics will be calculated by planned time point based on the worst value of the subject at that planned time point (or assigned to that planned time point).

Possibly clinically significant abnormal laboratory values are only those identified either in the Investigator's comments or at the RPM at the latest. It is the Investigator's responsibility to decide whether a lab value is clinically significant abnormal or not. Standard or project-specific rules for flagging clinically significant values in an automated manner will not be applied in this study.

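### SAP Table 6.1: 1 ends the Part 1 on-treatment phase at the planned hour of the Day 15 laboratory panel, so for completers only Day 8 reaches the laboratory summaries as a full post-dose panel

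*SAP*

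**What the plan says.** **Phase limits.** SAP 6.1 defines three phases for adverse events, laboratory data and vital signs. In Part 1 the on-treatment phase runs from dosing, inclusive, to "Date/time of administration of study drug + REP (14 days * 24 h", exclusive. Follow-up begins at that same instant, inclusive. Technical detail is left to the ADS Plan, which is not among the documents.

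**Which time is compared.** Protocol 7.3.4 assigns laboratory and similar measurements "based on the actual treatment at the planned time of the measurement" and adverse events by recorded onset. It places what lies between first intake and the end of the residual effect period (REP) in the treatment period, and events after the REP in follow-up. It leaves the exact intervals to the SAP. SAP 6.1 does not restate whether planned or actual time is used.

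**What is summarised.** Under SAP 7.8.2, laboratory statistics over time and differences from baseline "will be provided for the on-treatment phase". The same section adds: "Frequency tables of changes between baseline and last value on treatment with respect to the reference range will be presented".

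**When panels are taken.** The Part 1 Flow Chart plans set B on Day 8 (168:00) and Day 15 (336:00). Set C follows at the end-of-trial examination, 1 to 7 days after last discharge or before discharge on Day 50. Footnote 16 limits the other post-dose laboratory marks to haematocrit, with SARS-CoV-2 PCR where footnote 17 applies.

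**The concern.** The phase limit and a planned sampling time coincide to the hour, and the SAP resolves the tie by excluding the sample. The Day 15 panel is the last in-house laboratory assessment before Part 1 subjects are discharged. It is taken just as the 14-day REP closes. Excluding it means that the value labelled as last on treatment comes from Day 8, half-way through the phase. A laboratory change that developed in the second week would appear in the individual listings but not in the descriptive statistics or the shift table. Part 1 has 8 subjects and a purely descriptive analysis, so these tables are the main laboratory summary.

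**Working it through.** **The plan's own figure.** The REP is 14 days, and 14 × 24 h = 336 h. Protocol 1.2.2 bases it on an effective half-life of 50 to 70 h. The rule used is not stated. A five-half-life rule (an assumption) gives 5 × 50 / 24 = 10.4 days to 5 × 70 / 24 = 14.6 days, so 14 days is consistent with its stated basis. The length of the REP is not the problem.

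**Classifying the Part 1 samples by planned time t.** As written, a sample is on treatment if t < 336 h. With an inclusive end it is on treatment if t ≤ 336 h.

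| Planned sample | t (h) | Content | t < 336 | t ≤ 336 |
|---|---|---|---|---|
| Day 1 | 1, 4, 8 | haematocrit only | on treatment | on treatment |
| Day 2 | 24 | haematocrit, PCR | on treatment | on treatment |
| Day 8 | 168 | set B | on treatment | on treatment |
| Day 15 | 336 | set B | **follow-up** | **on treatment** |
| Weekly returns, if needed | 485 and later | haematocrit, PCR | follow-up | follow-up |
| End of trial, completers | 360 at the earliest (Day 16) | set C | follow-up | follow-up |

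**Count of full scheduled post-dose panels for completers.** There are three: Day 8, Day 15 and end of trial. As written, 1 of 3 is on treatment; with an inclusive end, 2 of 3. The last on-treatment value sits at 168 h as written, which is 168 / 336 = 50% of the way through the phase. With an inclusive end it sits at 336 h.

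**If actual times were used.** Protocol 6.1 allows laboratory tests on this day a deviation of ±90 min, so 336 ± 1.5 h = 334.5 to 337.5 h. A sample drawn at 335.5 h would be on treatment and one drawn at 336.5 h would be follow-up. The same visit could then contribute some subjects to the summaries and not others.

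**Same check for Part 2.** The limit is "Date/time of last administration of study drug + REP (14 days * 24 h", again exclusive. The last dose is planned at 480 h, so the phase ends at 480 + 336 = 816 h (Day 35). Set B panels on Days 7, 14, 21 and 27 (144, 312, 480 and 624 h) all fall before it, and set C on Day 62 (61 × 24 = 1464 h) falls well after it. No laboratory panel is planned at 816 h, so there is no collision.

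**The case against.** **The data are not lost.** SAP section 7 lists all individual values, and SAP 7.8.2 highlights those outside the reference range and reports clinically relevant laboratory findings as adverse events. SAP 7.8.3 does not confine vital-sign summaries to the on-treatment phase, so Day 15 vital signs are not affected in the same way. All of this stands and keeps the point small. One limit remains: an adverse event with recorded onset at or after 336 h is itself classed as follow-up, and the main adverse event displays "will present results for the on-treatment phase only".

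**The ADS Plan may settle the matter.** It may, and it cannot be checked here. But the planned-time rule in protocol 7.3.4 gives the result above, and the obvious alternative, actual times, exchanges a clean exclusion for a possible split by minutes. Only an explicit exception for this visit would help, and SAP 6.1 is the place for it.

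**The SAP is entitled to set the limit.** Protocol 7.3.4 does delegate the intervals. Even so, its wording sends to follow-up what occurs after the REP. A panel planned exactly at the end of the REP is not after it, so the exclusive end is tighter than the protocol needs. SAP section 4 reports no departure from the protocol.

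**A stronger reading to avoid.** A reader might infer that the 14-day REP is itself too short, because protocol 1.2.1 says that late sampling "revealed another phase with low plasma concentrations and long terminal half-life of about 200 h". The documents do not support that. Protocol 1.2.2 describes the REP thus: "This is the period after the last dose with measurable drug levels and/or pharmacodynamic effects is still likely to be present". The and/or means that measurable drug is not a required criterion. Protocol 1.2.1 also deals with the late phase directly: less than 20% of AUC lies beyond 192 h, and no marked contribution to accumulation is expected. Those data come from 200 mg with food, not the 100 mg fasted solution of Part 1.

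**Conclusion.** The point holds for the Part 1 laboratory summaries. For completers, and with measurements assigned by planned time, 1 of 3 full scheduled post-dose panels is summarised, and the last on-treatment value is the Day 8 value at 168 h. This follows from clock arithmetic on the stated rules and needs no pharmacokinetic assumption. It does assume that the unseen ADS Plan makes no exception for this visit.

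Two further inferences would go too far. First, the end-of-trial panel is not outside the phase for everyone. Protocol 3.3.4 and 6.2.3 call for an end-of-trial examination at early discontinuation, so a subject leaving Part 1 before 336 h could have an on-treatment set C panel. Second, the point does not extend to Part 2, where four of five panels are summarised and the Day 62 panel is ordinary follow-up.

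No effect on subject safety or on the pharmacokinetic endpoints is shown. Severity: minor, a free improvement.

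**What to change.** In SAP 6.1, add that laboratory data and vital signs are assigned to phases by planned time, as protocol 7.3.4 provides, and that Part 1 measurements planned at 336:00 belong to the on-treatment phase (an inclusive end for that visit). Align the ADS Plan. The 14-day REP, the Part 2 limits and the assignment of adverse events by recorded onset can stay as they are.

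The result is that 2 of 3 full panels enter the Part 1 laboratory tables, and the shift table runs to 336 h instead of 168 h. The cost is one sentence in the SAP, with no new visit, sample or table and no protocol amendment.

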6.2 IMPORTANT PROTOCOL DEVIATIONS

Consistency check listings (for identification of deviations from time windows) and a list of protocol deviations (e.g. deviations in drug administration, in blood sampling times, etc.) will be provided to be discussed at the RPM. At this meeting, it will be decided whether a discrepant data value can be used in the analyses or whether it must be corrected in the clinical database. Each protocol deviation must be assessed to determine whether it is an iPD. For definition of iPDs, and for the process of identification of these, refer to the BI reference document "Identify and Manage Important Protocol Deviations (iPD)" (2).

If any iPDs are identified, they are to be summarised into categories and will be captured in the decision log. Categories which are considered to be iPDs in this trial are defined in the DV domain. If the data show other iPDs, the definition in the DV domain will be supplemented accordingly by the time of the RPM.

iPDs will be summarized and listed. In the DV domain it is also specified which kind of iPDs could potentially lead to exclusion from which analysis set. The decision on exclusion of subjects from analysis sets will be made at the RPM at the latest after discussing exceptional cases and implications for the analyses.

Non important Covid-19 related protocol deviations will be listed.

6.3 SUBJECT SETS ANALYSED

All entered subjects who received study medication will be included in the safety analysis and in the PK analysis depending on the availability of measurement values, and on their adherence to the CTP.

The following subject sets will be defined for statistical analysis:

- **Treated set (TS):**
This subject set includes all subjects entered the study who were documented to have received at least one dose of study drug.
- **Pharmacokinetic parameter set (PKS):**
This subject set includes all subjects in the TS who provide at least one primary or secondary PK parameter that was not excluded because of iPDs relevant to the statistical evaluation of PK endpoints as defined in Section 7.3 of the CTP.

The two trial parts (Part 1 and Part 2) will be analysed separately. Therefore, the two analysis sets will be split into TS/PKS of Part 1 and TS/PKS of Part 2.

- The discussion of all exceptional cases and problems and the decisions on the allocation of subjects to analysis sets will be made at latest at the RPM.

Table 6.3: 1 Subject sets analysed

Class of endpoint	Subject set	
	TS	PKS
Disposition	X	
IPDs	X	
Demographic/baseline endpoints	X	
Primary and secondary PK endpoints		X
Further PK endpoints		X
Safety parameters and treatment exposure	X	

6.5 POOLING OF CENTRES

This section is not applicable, because the trial is performed in only one centre.

6.6 HANDLING OF MISSING DATA AND OUTLIERS

Data of screened subjects who were withdrawn from the trial prior to first administration of any study drug will not be reported in the CTR.

Data of subjects who failed to complete all periods of the study (dropouts or withdrawals) will be reported in the CTR as far as their data are available. All withdrawals will be documented and the reason for withdrawal reported in the CTR.

CTP Section 7.5.1: *It is not planned to impute missing values for safety parameters.*

One exception where imputation might be necessary for safety evaluation are AE dates. Missing or incomplete AE dates are imputed according to BI standards (3).

Missing data and outliers of PK data are handled according to BI standards (4) and (5)

CTP Section 7.5.2: *PK parameters that cannot be reasonably calculated based on the available drug concentration-time data will not be imputed.*

6.7 BASELINE, TIME WINDOWS AND CALCULATED VISITS

The last non-missing value determined prior to first BI 1358894 administration will be defined as baseline (in both parts).

Time windows are defined in Section 6.1 of the CTP. Adherence to time windows will be checked at the RPM.

7. PLANNED ANALYSIS

The format of the listings and tables will follow the BI guideline "Reporting of clinical trials and project summaries" (6)

The individual values of all subjects will be listed. Listings will be sorted by treatment group, subject number and visit (if visit is applicable in the respective listing). AE listings will be sorted by treatment group, subject number and AE onset date (see [Section 7.8.1](#) below for details). The listings will be contained in Appendix 16.2 (SDL) of the CTR.

If not stated otherwise, the data of Part 1 and Part 2 will be analysed separately.

The following standard descriptive statistical parameters will be displayed in summary tables of continuous variables:

N	number of non-missing observations
Mean	arithmetic mean
SD	standard deviation
Min	minimum
Median	median
Max	maximum

For plasma concentrations as well as for all PK parameters the following descriptive statistics will additionally be calculated:

CV	arithmetic coefficient of variation
gMean	geometric mean
gCV	geometric coefficient of variation

For PK parameters the following descriptive statistics will additionally be calculated:

P10	10 th percentile
Q1	1 st quartile
Q3	3 rd quartile
P90	90 th percentile

The data format for descriptive statistics of plasma concentrations will be identical with the data format of the respective concentrations. The descriptive statistics of PK parameters will be calculated using the individual values with the number of decimal places as provided by the evaluation program. Then the individual values as well as the descriptive statistics will be reported with three significant digits in the CTR.

Tabulations of frequencies for categorical data will include all possible categories and will display the number of observations in a category as well as the percentage (%) relative to the respective treatment group. Percentages will be rounded to one decimal place. The category missing will be displayed if and only if there actually are missing values. Percentages will be based on all subjects in the respective subject set whether they have non-missing values or not.

7.1 DEMOGRAPHIC AND OTHER BASELINE CHARACTERISTICS

Only descriptive statistics are planned for this section of the CTR.

7.2 CONCOMITANT DISEASES AND MEDICATION

Concomitant diseases will be coded according to the most recent version of MedDRA. Concomitant medication will be coded according to the most recent version of the World Health Organisation – Drug Dictionary. Concomitant non-drug therapies will be coded according to the most recent version of MedDRA.

A medication will be considered concomitant, if it

- is ongoing at the time of first study drug administration, or
- starts within the analysis phase of the respective treatment (see [Section 6.1](#) for a definition of treatments and analysis phases).

The relevance of the concomitant therapies to the evaluation of PK will be decided no later than at the RPM.

CTP Section 7.3.4: *Previous and concomitant therapies will be presented per treatment group without consideration of time intervals and treatment periods.*

Only descriptive statistics are planned for this section of the CTR.

